8 STUDY SUBJECTS

Patient disposition for expansion Phase will be summarized by each cohort and total. The total number of all screened patients will be used and presented in the column header and serves as the denominator for calculating percentage. Following will be presented in the disposition table:

- The number and percentage of patients enrolled
- The number and percentage of patients screened failures
- Reasons for screen failures
- The number and percentage of patients dosed with ferumoxytol (Ferumoxytol Safety Population)
- The number and percentage of patients dosed with MM-398 (MM-398 Safety Populations)

In addition, patient disposition will be summarized using safety population:

- The number and percentage of patients included in Efficacy Evaluable Population
- The number and percentage of patients included in PD population
- The number and percentage of patients discontinued from treatment early by reasons for discontinuation
- The number and percentage of patients discontinued from study (i.e. did not complete study to 30-day follow-up) early by reasons for discontinuation.

8.1 Protocol Deviations

Prior to database lock, Important Protocol Deviations (IPDs) will be identified through programmatic checks of study data, as well as through review of selected data listings. The potential IPDs to be reviewed include, but are not limited to, patients who:

- Did not meet key inclusion/exclusion criteria
- Received any disallowed concomitant medication during the treatment period
- Other

Individual IPDs will be presented in a data listing. The number and percentage of patients with IPDs will be summarized by study phases and overall.

8.2 Inclusion and Exclusion Criteria

Violations of key inclusion and exclusion criterion will be included in protocol violation tabulations. Inclusion criteria will be listed for non-screen failures who did not meet criteria. Exclusion criteria will be listed for non-screen failures who met criteria.

9 DEMOGRAPHICS AND BASELINE CHARACTERISTICS

Demographics and baseline data will be presented by Pilot and Expansion Phases, where patients in expansion phases will be summarized by each cohort and total. No formal statistical analysis will be performed on these data.

Summaries will be created for the following patient characteristics:

- Patient demographics (each analysis population)
- Baseline disease characteristics (each analysis population)
- Prior therapies (each analysis population)
- Medical history and pre-existing conditions (MM-398 safety population)
- Concomitant therapies (MM-398 safety population)

9.1 Demographics

A summary of the number and percentage of patients in each category for gender, race and ethnicity will be presented. Age (years), height (cm), weight (kg), body mass index (BMI) and body mass index group will be summarized using summary statistics for continuous variables.

9.2 Baseline Characteristics

The following baseline characteristics will be summarized, where applicable, by study phases and cohorts within expansion phase:

- ECOG Status
- UGT1A1*28 allele (Homozygous 7/7, non-Homozygous)
- Cancer site
- Status of brain metastases
- Time since histo-pathological diagnosis
- Stage at diagnosis
- Time since metastatic diagnosis

9.3 Prior Anti-Cancer Therapy, Radiotherapy, and Surgery

The following prior anticancer therapy (related to study indication) characteristics will be tabulated by study phases and cohorts within expansion phase:

- Type of prior anti-cancer therapy
- Administration setting
- Number of prior anti-cancer regimens

Time since last anti-cancer therapy prior to study enrollment will be summarized.

Prior radiotherapies and prior surgeries related to study indication will be tabulated, with further tabulation by location and by reason for treatment/procedure.

9.4 Medical History and Pre-existing Conditions

Patient medical history will be coded by System Organ Class (SOC) and Preferred Term (PT) using the Medical Dictionary for Regulatory Activities (MedDRA), version 17 or higher. Prior medical history will be tabulated.

9.5 Prior and Concomitant Therapies

Summaries of all medications taken during the course of the study will be recorded. Medications will be standardized based on the World Health Organization Drug Classification Dictionary

(WHODRUG, version 01DEC2017 WHODDE) Anatomic Therapeutic Class (ATC) Level II preferred term.

All medications (excluding study drug) taken during the course of the study with a start date or an end date on or after the date of the first dose of MM-398, or marked as ongoing will be considered concomitant. Medications stopped prior to the date of the first dose of study drug will be considered as prior medication. Prior medications will be flagged on the concomitant medication listing.

The number and percent of patients taking medications will be summarized by study period and WHODRUG ATC Level II and preferred term. In the tabular presentation, medications will be sorted by frequency and then alphabetically by preferred term. If a patient has more than one qualifying record for a medication, the patient will be counted only once in the tabulation.

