6.1.3 Administration of MM-398

MM-398 will be administered by intravenous (IV) infusion over 90 minutes at a dose of 60 mg/m² every two weeks. The dose of MM-398 should be escalated to 80 mg/m² every two weeks depending on patient tolerance. The first cycle Day 1 is a fixed day; subsequent doses should be administered on the first day of each cycle +/- 2 days.

Prior to administration, the appropriate dose of MM-398 must be diluted in 5% Dextrose Injection solution (D5W) to a final volume of 500 mL. Care should be taken not to use any

diluents other than D5W or 0.9% sodium chloride USP, to a final volume of 500 mL. MM-398 can be administered using standard intravenous administration bags and tubing.

The actual dose of MM-398 to be administered will be determined by calculating the patient's body surface area (BSA) at the beginning of each cycle. A +/- 5% variance in the calculated total dose will be allowed for ease of dose administration. Since MM-398 vials are single use vials, site staff must not store any unused portion of a vial for future use and must discard all unused portions of the product.

If a patient experiences an infusion reaction, or any adverse event deemed as related by the investigator to ferumoxytol, MM-398 should be held until the event is grade 1 or resolved.

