9.1.3 Adverse Events of Special Interest

For this protocol the collection of Adverse Events of Special Interest (AESI) will be reported following serious adverse event reporting procedures as described below.

For this protocol, a specific AESI includes notification and collections of hypersensitivity reactions associated with the administration of ferumoxytol and will follow Serious Adverse Event notification procedures. Hypersensitivity reaction reports including anaphylaxis/anaphylactoid reactions should include individual signs and symptoms, time to onset, time to resolution and any intervention or medication given for the treatment thereof.

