6 ANALYSIS POPULATIONS

- **Screened population:** This population includes all patients screened (i.e. who signed the informed consent).
- **Safety population:** This population includes all patients receiving at least one dose of MM-398 or ferumoxytol. If ferumoxytol safety population is different from MM-398 safety population, safety analysis will be performed separately on both populations.

Depending upon patients receiving MM-398 and not ferumoxytol and vice versa, the safety population may be expanded in order to not dilute any adverse event rate:

- Ferumoxytol safety population: any patient receiving ferumoxytol. All analyses using this population will be based on the treatment actually received.
- MM-398 safety population: all patient receiving at least one dose of MM-398. All analysis using this population will be based on the treatment actually received.
- **Efficacy evaluable population**: This population includes all patients receiving at least one dose of MM-398. All statistical analyses of data on non-imaging related efficacy analyses will be performed using efficacy evaluable population.
- **Pharmacodynamic (PD) evaluable population**: This population includes all efficacy evaluable patients with the following: a) pre-treatment FMX-MRI scan(s) and b) radiological scans at 8 weeks. All statistical analyses of data on imaging related efficacy analyses will be performed using PD evaluable population.
- **Pharmacokinetic (PK) population**: This population includes patients receiving at least one dose of MM-398, and blood samples at the predefined timepoints adequately collected (with no major protocol deviations affecting the PK variables & with sufficient number of plasma concentrations to estimate the main PK parameters (C_{max}, AUC)). PK analysis will be documented in a separate SAP.

The term ‘All Screened Patients’ will be used to describe the set of all patients who signed informed consent, including patients who failed screening and any others who initiated screening.

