7.6.3 Study Periods

For the evaluation of safety, assessments will be assigned to study periods. These will be:

- Ferumoxytol safety period: from time of the first dose of ferumoxytol to the time of the first dose of MM-398. If an observation contains a date only, then the corresponding ferumoxytol safety period is the time from the date of the first dose of ferumoxytol to the day before the date of the first administration of MM-398. If the patient does not receive MM-398, the ferumoxytol safety period ends at 30 days after the date of the ferumoxytol dose.
- MM-398 safety period: from time of the first dose of MM-398 to 30 days after the date of the last study drug administration of MM-398. If an observation contains a date only, then the corresponding MM-398 safety period begins on the date of the first administration of MM-398.
- Events/observations will be assigned to study periods based on the start date or date and time if time is available.

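### The SAP dates concomitant medication from the first MM-398 dose and tabulates it only in MM-398-treated patients, so medicines confined to the ferumoxytol period are misclassified or missing from the table

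*SAP*

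**What the plan says.** SAP 9.5 treats a non-study medication as concomitant if it was taken "with a start date or an end date on or after the date of the first dose of MM-398, or marked as ongoing". Its companion rule is "Medications stopped prior to the date of the first dose of study drug will be considered as prior medication", and here the drug is not named. The same section says that use will be summarised by study period, and that prior medications are flagged on the concomitant medication listing.

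SAP 9 assigns the summary to one population: "Concomitant therapies (MM-398 safety population". SAP 6 defines two drug-specific populations: "MM-398 safety population: all patient receiving at least one dose of MM-398" and "Ferumoxytol safety population: any patient receiving ferumoxytol". The second is not used for this table.

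SAP 7.6.3 defines a ferumoxytol safety period running "from time of the first dose of ferumoxytol to the time of the first dose of MM-398", or to 30 days after ferumoxytol if MM-398 is never given. It assigns events and observations to periods by start date. Protocol 4.2 has MM-398 begin within 7 days of ferumoxytol. For ferumoxytol-related events, protocol 6.1.3 says "MM-398 should be held until the event is grade 1 or resolved", and protocol 6.2.3 has a similar hold. Protocol 9.1.3 makes ferumoxytol hypersensitivity an adverse event of special interest, whose report must include "any intervention or medication given for the treatment thereof". Protocol 10.7 counts treatment-emergent events from the first dose of either drug.

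**The concern.** Patients are on study treatment from the ferumoxytol infusion, but the medication clock starts only at MM-398. The interval between the two drugs is when an acute ferumoxytol reaction would be treated. A short course begun and finished in that interval cannot meet the SAP 9.5 definition of concomitant. A patient who reacts and never goes on to MM-398 is outside the table whatever the dates.

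Adverse events and the medicines given for them would then run on different clocks. A reaction would be counted in the ferumoxytol period, while its treatment would be absent from the concomitant table for that period. Under one reading of *study drug* the treatment would be labelled as preceding study drug. Protocol 10.5 plans to tabulate prior medications next to baseline characteristics, so treatment given on study could appear there. Safety of MM-398 in the presence of ferumoxytol is a secondary objective in all phases, so the tables should be consistent on this point.

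**Working it through.** The plan gives no figure on this point. The check is to apply the SAP 9.5 rule to test records.

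**Which drug is *study drug*?** SAP 7.1 supports two readings. It defines the pre-treatment period by the first administration of ferumoxytol or MM-398 respectively, but it sets the reference start date at MM-398. Both readings are run below.

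**Rule as written.** Concomitant: start ≥ first MM-398 date, or end ≥ first MM-398 date, or ongoing. Prior: end < first study drug date.

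**Test records.** Ferumoxytol on Day 1; MM-398 on Day 7 or never.

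| Medicine taken | MM-398 | *Study drug* = MM-398 | *Study drug* = ferumoxytol | Patient in SAP 9 table? |
|---|---|---|---|---|
| Day 1 only | Day 7 | prior | no class | yes |
| Days 1–3 | Day 7 | prior | no class | yes |
| Days 1–8 | Day 7 | concomitant | concomitant | yes |
| Day 1, ongoing | Day 7 | concomitant | concomitant | yes |
| Day 1 only | never | no class | no class | no |
| Day 1, ongoing | never | concomitant | concomitant | no |

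In the first two rows the end date (1 or 3) is below 7, so the medicine is not concomitant. It is below the MM-398 date, hence prior under that reading. It is not below Day 1, hence unclassified under the other. Rows 3 and 4 are classed correctly. In the last two rows the patient has no MM-398 dose and is outside the tabulated population.

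**Consistency with the rest of the plan.**
- The by-period summary in SAP 9.5 implies a ferumoxytol-period column, but the definition removes every medicine that both starts and stops within that period.
- SAP 12 presents safety for each safety population by its own study period, and protocol 10.7 starts the adverse event clock at either drug. The medication table does neither.

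**Illustrative scale.** This assumes that the background ferumoxytol rates in protocol 2.2.2 apply here, with the approximate total enrolment of 45 from protocol 4.1. Expected reactions = 45 × rate; chance of at least one = 1 − (1 − rate)^45.
- Serious, 3/1,726: 45 × 3/1,726 = 0.08; chance about 7.5%.
- Moderate to severe, 26/1,014: 45 × 26/1,014 = 1.15; chance about 69%.
- Other reactions potentially associated with hypersensitivity, 63/1,726: 45 × 63/1,726 = 1.64; chance about 81%.

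These count reactions, not misclassified medicines. The documents do not say what share of reactions would be treated with a course that ends before MM-398.

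**The case against.** The best defence is that the tabulation sentence in SAP 9.5 speaks of medications generally and by study period, and the section opens with all medications taken during the study. With SAP 7.6.3, that can be read as intending a ferumoxytol-period table. This has some force for patients who go on to MM-398, but it does not reconcile the text: the definition still excludes medicines confined to the gap, and the SAP 9 population line still excludes patients who never receive MM-398.

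Several further objections stand in full and limit the point.
- A reader might infer that treatment of ferumoxytol reactions is lost. It is not. SAP 9.5 keeps prior medications on the listing with a flag, SAP 7.1 keeps data excluded from tables in the listings, protocol 9.1.3 puts treatment in the special-interest report, and protocol 9.2 records with each event whether drug treatment was required.
- A reader might infer that the severity of reactions is understated. The documents do not support this. Severity is CTCAE grade, tabulated under SAP 12.1 without using the medication table. That table is organised by drug class and preferred term and does not link a drug to an event.
- A reader might assume that reaction treatment always ends before MM-398. Protocol 6.1.3 and 6.2.3 let MM-398 proceed once the event is Grade 1 and say nothing about its treatment having stopped.
- The background rates come from other trials, and protocol 5.2 excludes patients with IV iron allergy or multiple drug allergies.

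**Conclusion.** The point holds as a misclassification in the descriptive medication tables. As written, a medicine confined to the interval between ferumoxytol and MM-398 is either prior or unclassified, depending on which drug *study drug* means. A patient given ferumoxytol but never MM-398 is missing from the concomitant table. Both follow from the SAP's text and need no assumption about rates.

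It goes no further than that. No efficacy result or adverse event rate changes. Medicines continuing to the first MM-398 dose, or marked ongoing, are handled correctly in patients who receive MM-398. On the assumed background rates, about 0.08 to 1.6 reactions would be expected in 45 patients, and the number of affected medication records could be smaller because not all reactions would involve a medicine confined to the gap. The case for changing the text is that the rule contradicts other parts of the plan and is cheap to correct.

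**What to change.** In SAP 9.5, define concomitant as any non-study medication with a start or end date on or after the first dose of ferumoxytol or MM-398, whichever came first, or ongoing. Define prior as stopped before that same date, naming the two drugs in place of *study drug*.

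Tabulate the ferumoxytol period in the ferumoxytol safety population and the MM-398 period in the MM-398 safety population, and change the SAP 9 population line to match.

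Add a rule that a medication counts in every period its dates overlap. Changing the reference date alone is not enough. SAP 7.6.3 assigns by start date, so a medicine begun before ferumoxytol and continued would fall in neither period, and one begun after ferumoxytol and continued would not appear under MM-398.

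The cost is a few sentences in the SAP, one reference date, the overlap rule in programming and the matching table shells. No new data are needed: protocol 6.4 requires all concomitant medications to be recorded, and the schedule in protocol 8.2 collects them on ferumoxytol Days 1 and 2 and at Day 1 of MM-398.

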9.6 Concomitant Procedures

Concomitant procedures will be presented in a listing which will include the procedure term (verbatim), date, indication (reason for the procedure), yes/no indicator of relationship to an adverse event, and findings from the procedure.

10 TREATMENT COMPLIANCE AND EXPOSURE

Treatment exposure will be summarized separately for ferumoxytol and MM-398. Exposure to ferumoxytol will be summarized by the amount of drug administered, both as mg/kg and total mg.

The following MM-398 exposure metrics will be summarized by cycle:

- summary statistics for the amount of drug administered, in mg/m^2
- summary statistics for the amount of drug administered, in mg
- number of patients with dose delay
- number of patients with dose reduction.

Overall exposure of MM-398 will be summarized by:

- frequency table of the total number cycles of doses administered
- summary statistics for treatment duration in weeks
- cumulative dose received, in mg/m^2
- cumulative dose received, in mg
- dose intensity, in $\text{mg}/\text{m}^2/\text{wk}$

11 EFFICACY ANALYSES

11.1 Primary Efficacy Endpoints:

The efficacy endpoints will be summarized for efficacy evaluable population and PD evaluable population by using descriptive statistics.

Pilot Phase:

- **Feasibility of FMX-MRI on identifying tumor associated macrophages (TAMs):**

FMX-MRI will be conducted on day 1 before and 1-4 h after intravenous ferumoxytol (FMX) administration, then after 24 h and/or 72 h. For the quality scan of FMX-MRI, scanner type (i.e. 1.5T), impact of scan quality on analysis (i.e. adequate for evaluation, suboptimal but completed for evaluation, or inadequate for evaluation), reasons for scan suboptimal/inadequate) and scan location (i.e. Body) will be assessed.

- **Tumor Levels of Irinotecan and SN-38:**

During pilot phase, two biopsies are collected on Day 4 of the ferumoxytol phase and two biopsies are collected three days after the first dose of MM-398. Tumor levels of irinotecan and SN-38 in core biopsy will be measured after MM-398 dosing.

Expansion Phase:

- **Feasibility of Ferumoxytol (FMX) Quantitation in Tumor Lesion**

Feasibility of ferumoxytol (FMX) quantitation in tumor lesion is also assessed through the acquisition of baseline and follow-up images of sufficient quality that enable quantitative analysis to be performed.

Eligible patients should have serial FMX-MRI scans prior to and following FMX infusion as determined by their scan group. After MRI acquisition, the R2* signal is used to calculate FMX levels in plasma, tumor lesions and reference tissue by comparison to a phantom-based standard curve.

- **The Relationship Between Ferumoxytol (FMX) tumor uptake and tumor response to MM-398**

FMX-MRI will be done for various tissues and at different timepoints. Corrected FMX uptake (post-baseline value - baseline value) will be recorded by each time point and tissues. Ferumoxytol uptakes will be associated with change in tumor lesion size.

11.2 Primary Efficacy Analysis:

Pilot Phase

In patients with NSCLC, CRC, TNBC, ER/PR positive breast cancer, pancreatic cancer, ovarian cancer, gastric cancer, GEJ adenocarcinoma or head and neck cancer, who are undergoing therapy with MM-398:

- To evaluate the feasibility of delayed ferumoxytol MRI (FMX-MRI) to identify tumor associated macrophages (TAMs)
The quality of FMX-MRI scan on impact of evaluation will be summarized descriptively by evaluation time points. For the quality scan of FMX-MRI, number of FMX-MRI scans obtained, number of scans accepted for evaluation, and scan location (i.e. Body) at each time point will be assessed. If there is more than one image data at the same timepoint for a patient, image data are averaged first before summarizing.

- To measure tumor levels of irinotecan and SN-38
Tumor levels of irinotecan and SN-38 during Pilot phase were assessed through tumor tissue biopsy. The data are summarized using descriptive statistics with n, min, max, mean 25th percentiles (Q1), 75th percentiles (Q3) and median per lesion. Tumor levels of irinotecan and SN-38 in core biopsy are reported in Merrimack Pharmaceuticals Synopsis Clinical Study Report MM-398-01-01-02, published on 18-Dec-2014 (Appendix X). No further analysis is required.

Expansion Phase

In patients with locally advanced or metastatic breast cancer:

- To further investigate the feasibility of ferumoxytol (FMX) quantitation in tumor lesions

Feasibility of ferumoxytol (FMX) quantitation in tumor lesion is assessed through the acquisition of baseline and follow-up images of sufficient quality that enable quantitative analysis to be performed. Sufficient quality is assessed by summarizing images that are adequate for evaluation, suboptimal but completed for evaluation, or inadequate for evaluation at each visit.

- To characterize the relationship between ferumoxytol (FMX) tumor uptake and tumor response to MM-398

Ferumoxytol uptakes will be associated with change in tumor lesion size. Corrected FMX results (ug/mL) from target lesion(s) at 24-hour scan is used to measure FMX tumor uptake. For the repeated scans performed at the same timepoint, the FMX tumor uptake will be averaged first before summarizing. For patient with multiple target lesions, average corrected FMX results should be used for analysis. FMX uptake will be classified as 'low tumor uptake' or 'high tumor uptake' using overall median as cutoff. Change in tumor size is used to assess tumor response to MM-398. For patient with multiple target lesions, the best change in tumor size achieved should be used. The relationship between dichotomous FMX tumor uptake classification and tumor response to MM-398 will be assessed using Fisher's exact test.

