MM-398 is irinotecan encapsulated in a nanoliposomal delivery system. Nanoliposome delivery reduces systemic exposure and increases drug accumulation within a tumor. Tumor associated macrophages (TAMs) appear to play a key role in the deposition, retention and activation of MM-398 within the tumor microenvironment. Ferumoxytol is an approved therapy that is indicated for the treatment of iron deficiency anemia in adult patients with chronic kidney disease; however a growing number of cancer patients without iron deficiency are being administered ferumoxytol as an imaging agent to visualize macrophage content and vasculature [1], [2]. This pilot study will evaluate the feasibility of measuring TAMs by utilizing ferumoxytol MRI (FMX-MRI) as an imaging agent and will also measure corresponding MM-398 metabolite drug levels, and their correlation. If successful, future studies will correlate macrophage profiling using FMX-MRI as a potential predictive biomarker for patients treated with MM-398.

To maximize the information from this study, patients that are most likely to achieve the objectives of the study will be enrolled. Although the first three patients enrolled in the study can have any solid tumor, subsequent patients will be limited to a subset of indications. Selection of these indications is based on the expected higher levels of tumor-associated macrophages, the potential sensitivity to irinotecan based on clinical experience and/or the presence of the prodrug converting carboxyl esterase enzymes (CES) and the amenability to imaging and biopsy collection. These indications include colorectal cancer (CRC), non-small cell lung cancer (NSCLC), triple negative breast cancer (TNBC), estrogen receptor and/or progesterone receptor (ER/PR) positive breast cancer, pancreatic cancer, ovarian cancer, gastric cancer, gastroesophageal junction (GEJ) adenocarcinoma and head and neck cancer. No more than three patients with ER/PR positive breast cancer can be enrolled in the Pilot Phase of the study and similar restrictions may be placed on other tumor types to ensure a heterogeneous population at study end.

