3.1 Primary Objectives

Pilot Phase (Completed)

In patients with NSCLC, CRC, TNBC, ER/PR positive breast cancer, pancreatic cancer, ovarian cancer, gastric cancer, GEJ adenocarcinoma or head and neck cancer, who are undergoing therapy with MM-398:

- To evaluate the feasibility of delayed ferumoxytol MRI (FMX-MRI) to identify tumor associated macrophages (TAMs)
- To measure tumor levels of irinotecan and SN-38

Expansion Phase:

In patients with locally advanced or metastatic breast cancer:

- To further investigate the feasibility of ferumoxytol (FMX) quantitation in tumor lesions
- To characterize the relationship between ferumoxytol (FMX) tumor uptake and tumor response to MM-398

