7.3 Tissue Collection

7.3.1 Fresh Tumor Biopsies

7.3.1.1 Pilot Phase Biopsies

Two biopsies will be collected on Day 4 of the ferumoxytol phase and two biopsies will be collected three days after the first dose of MM-398.

On Day 4 of the ferumoxytol phase, the lesion(s) selected for biopsy will be based on the results of the FMX-MRI obtained on Days 1, 2 and 4. The first core biopsy will be in the region of the tumor that shows the greatest signal change based on FMX-MRI and the second core biopsy will be taken from the region that shows the least signal change based on FMX-MRI.

On Cycle 1 Day 4 of the MM-398 Treatment phase, the lesion(s) selected for biopsy will be based on the results of the FMX-MRI obtained on Days 1, 2 and 4 of the ferumoxytol phase. The post-treatment biopsies will be collected from a previously non-biopsied lesion. The first core biopsy will be in the region of the tumor that shows the greatest signal change on either the T2* or T1 sequences, based on FMX-MRI. The second core biopsy will be taken from the region that shows the least signal change based on FMX-MRI, avoiding obvious areas of necrosis.

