10.9 Pharmacodynamic Marker Analysis

Spearman pairwise correlations will be computed between the following measurements obtained from the Pilot Phase of the study:

- FMX-MRI levels
- Tumor associated macrophage levels
- Tumor irinotecan levels
- Tumor SN-38 levels

Graphical and regression methods will be used to explore potential relationships among correlated measurements. In addition, relationships between pharmacodynamics markers and efficacy response will be evaluated in an exploratory manner in both the Pilot Phase and Expansion phases of the study.

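### The Pilot primary endpoint is labelled as identifying tumor associated macrophages, but its analysis covers only scan acquisition and quality, so it can support technical feasibility and nothing about macrophages

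*SAP*

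**What the plan says.** Protocol 3.1 gives the first Pilot primary objective as "To evaluate the feasibility of delayed ferumoxytol MRI (FMX-MRI) to identify tumor associated macrophages (TAMs"). The background (Protocol 2) says the pilot will "evaluate the feasibility of measuring TAMs by utilizing ferumoxytol MRI (FMX-MRI) as an imaging agent".

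SAP 11.1 carries this over as a primary endpoint headed "Feasibility of FMX-MRI on identifying tumor associated macrophages (TAMs"). The variables under that heading begin "For the quality scan of FMX-MRI, scanner type (i.e. 1.5T), impact of scan quality on analysis" and continue with the reasons for suboptimal or inadequate scans and the scan location. SAP 11.2 gives the analysis: "The quality of FMX-MRI scan on impact of evaluation will be summarized descriptively by evaluation time points", and "number of FMX-MRI scans obtained, number of scans accepted for evaluation, and scan location (i.e. Body) at each time point will be assessed".

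Macrophage data appear elsewhere:

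- Protocol 10.9 lists "Tumor associated macrophage levels" among four Pilot measurements, alongside FMX-MRI, for which Spearman pairwise correlations are to be computed.
- SAP 11.3.2.5, under the imaging-related secondary analyses, offers a scatter plot of FMX-MRI against TAM level and tumor drug levels. It names no coefficient and no interval.
- SAP 13.1 leaves marker work as optional and post hoc.

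**The concern.** The label and the content of the endpoint answer different questions. Counting acceptable scans shows whether images can be obtained and read. It does not show whether the signal in them reflects macrophages. Protocol 2.2.3 makes clear that the second question was the open one: it justifies a pilot by the need to learn whether FMX-MRI detects a TAM signal.

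If the report follows the SAP as written, good image quality will appear under a heading about identifying macrophages, and readers may take it as evidence of that. The label also carries forward. SAP 11.3.2.5 evaluates the value of FMX-MRI in directing biopsy partly by summarising its feasibility for identifying TAMs, so that secondary objective would inherit a result with no macrophage data in it.

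**Working it through.** **Step 1. Inputs to the primary summary.** The documents attach no power calculation, threshold or success rate to this endpoint, so there is no plan figure to reproduce. The check is a comparison of text.

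| Item | Where | Uses a TAM measurement? |
|---|---|---|
| Scanner type | SAP 11.1 | No |
| Quality category, and reasons if suboptimal or inadequate | SAP 11.1 | No |
| Scan location | SAP 11.1, 11.2 | No |
| Scans obtained | SAP 11.2 | No |
| Scans accepted for evaluation | SAP 11.2 | No |
| Averaging of multiple images at one time point | SAP 11.2 | No |

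The averaging rule hints that some image value may be summarised. It names none, and nothing is compared with TAM level. None of the listed quantities involves the relation between FMX signal and TAM level, so the summary cannot inform it. This needs no assumption about scan acceptance rates.

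**Step 2. Where FMX and TAM are compared.** Protocol 10.9 plans a Spearman correlation plus graphical and regression methods. SAP 11.3.2.5 plans a scatter plot only. The plot uses corrected FMX across all of a patient's scanned lesions, so it is not tied to the lesion that was biopsied.

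**Step 3. What the restored estimate could show.** Inputs: Pilot size 12 to 20 (SAP 4); one FMX value and one TAM value per patient; an observed Spearman correlation of 0.5, which is an illustrative assumption. The interval uses Fisher's z with standard error 1.03/√(N−3):

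- z = atanh(0.5) = 0.549.
- N = 12: SE = 1.03/√9 = 0.343. Limits on the z scale are 0.549 ± 1.96 × 0.343 = −0.124 and 1.222. Back-transformed: **−0.12 to 0.84**.
- N = 20: SE = 1.03/√17 = 0.250. Limits are 0.060 and 1.039. Back-transformed: **0.06 to 0.78**.

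A simulation of 4,000 bivariate normal samples with no true relation gave sample Spearman values mostly (central 95%) between −0.58 and 0.58 at N = 12, and between −0.44 and 0.45 at N = 20. At the lower sample size, an observed 0.5 would therefore not be unusual under no relation.

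**Step 4. Tissue available.** Protocol 7.3.1.1 takes two Day 4 cores: "The first core biopsy will be in the region of the tumor that shows the greatest signal change based on FMX-MRI", and the second from the region of least change. That would give a within-patient contrast if both cores were assayed for TAMs. The documents do not say that they were. They also refer to one or more lesions, so the two cores need not come from the same lesion.

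**The case against.** The best defence is that the documents separate feasibility (primary) from correlation (secondary) on purpose, and that the SAP treats feasibility as image acquisition in both phases. In the Expansion Phase this fits, because that objective concerns quantitation of ferumoxytol. The Pilot objective is worded differently, around macrophages, so the defence explains the choice of summary but does not justify the label. It does argue against moving the TAM comparison up to primary, and that stands.

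Several stronger readings are tempting and are not supported:

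- *The trial never compares FMX-MRI with TAMs.* It does, through Protocol 10.9 and the SAP scatter plot. The shortfall is that the SAP drops the estimate. Protocol 10.3 lets the SAP modify planned analyses, so this is not itself a breach.
- *A useless marker would pass the endpoint with some calculable high probability.* The plan has no pass mark: SAP 4 says results are descriptive and SAP 7.4 says there is no testing. Any such probability would describe a rule the reader had invented.
- *The paired-core data are already in hand.* The documents do not establish this (Step 4).
- *The TAM comparison should become the primary analysis.* The Pilot is complete, and SAP 11.2 cites a synopsis study report from December 2014. Protocol 10.3 requires major changes to the primary endpoint or its analysis to be reflected in an amendment. Whether that report already contains FMX-TAM results cannot be seen from these documents.

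**Conclusion.** The concern holds in a limited form. The Pilot primary summary, as listed in SAP 11.1 and 11.2, supports technical feasibility of FMX-MRI acquisition. It does not support a conclusion about identifying TAMs, because no TAM measurement enters it. The SAP's only FMX-TAM comparison is a secondary plot with no estimate, although the protocol plans a Spearman correlation.

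This rests on the wording of the two documents and not on a modelled error rate. The numerical part is the precision of the restored estimate, and it assumes one pair of values per patient, an observed correlation of 0.5 and all 12 to 20 patients contributing. Fewer usable TAM results would widen the intervals further.

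**What to change.** 1. In SAP 11.1 and 11.2 (Pilot), relabel the scan summary *technical feasibility of FMX-MRI acquisition*, and state that it does not by itself support identification of TAMs. Carry the same wording into the biopsy-direction objective in 11.3.2.5.
2. In SAP 11.3.2.5, restore the Spearman correlation of FMX-MRI with TAM level from Protocol 10.9, one value per patient, with a 95% confidence interval. Use delayed corrected FMX from the biopsied lesion where available, and name the time point: SAP 3.1 lists Pilot scans to 24 hours, while 11.1 allows 24 and/or 72 hours. State that any conclusion about identifying TAMs rests on this estimate.
3. Where both Day 4 cores have a TAM result, add the within-patient difference (greatest minus least signal) with a 95% confidence interval, as descriptive support, and report how many patients contribute.
4. Keep items 2 and 3 descriptive and under the existing secondary objective. Disclose that they were specified after the Pilot was completed.

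The cost is SAP wording and a small table, with no new patients, scans or biopsies. The quantities summarised for the primary endpoint do not change, but the sponsor should confirm that the relabelling is not a major modification under Protocol 10.3. The downside is a wide interval and a less favourable stated conclusion about TAMs.
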